1. LIST OF ABBREVIATIONS AND GLOSSARY OF TERMS

1.1. List of Abbreviations

AE	Adverse event
ARCI-49	Addiction Research Center Inventory 49
ATC	Anatomical Therapeutic Chemical
AUR-Q	Antibiotic Use for Respiratory Signs and Symptoms Questionnaire
BID	Twice per day
BMI	Body mass index
CF	Cystic fibrosis
CFQ-R	Cystic Fibrosis Questionnaire - Revised
CI	Confidence interval
COVID-19	Coronavirus-19 disease
CFRSD	Cystic Fibrosis Respiratory Symptom Diary
CFTR	Cystic fibrosis transmembrane conductance regulator
CRISS	Chronic Respiratory Infection Symptom Scale
CRP	High sensitivity C-Reactive protein
CSR	Clinical Study Report
DMC	Data Monitoring Committee
ECG	Electrocardiogram
ESR	Erythrocyte sedimentation rate
FEV1	Forced expiratory volume in 1 second
FVC	Forced vital capacity
IV	Intravenous
IWRS	Interactive Web Response System
mITT	Modified intent-to-treat
MMRM	Mixed model for repeated measures
PEx	Pulmonary exacerbation(s)
PK	Pharmacokinetic(s)

PP	Per protocol
SAP	Statistical Analysis Plan
SOC	System Organ Class
TEAE	Treatment-emergent adverse event
TMT	Trail Making Test

1.2. Glossary of Terms

Adverse event:	
Any untoward medical occurrence in a patient or a clinical investigation subject administered a pharmaceutical product and which does not necessarily have a causal relationship with this treatment.
 
An adverse event can therefore be any unfavorable and unintended sign (including an abnormal laboratory finding, for example), symptom, or disease temporally associated with the use of a medicinal (investigational) product, whether or not related to the medicinal (investigational) product. For marketed medicinal products, this also includes failure to produce expected benefits (i.e., lack of efficacy), abuse, or misuse.

Blinding:	A procedure in which 1 or more parties to the trial are kept unaware of the treatment assignment with the intent to reduce the risk of biased outcomes.
Completed:	Subject who completed the last protocol-defined visit.
Eligible:	Qualified for enrollment into the study based upon adherence to inclusion/exclusion criteria.
Study product:	A pharmaceutical form of an active ingredient or placebo being tested or used as a reference in a clinical trial.
Life-threatening:	The term “life-threatening” in the definition of “serious” refers to an event in which the subject was at risk of death at the time of the event; it does not refer to an event which hypothetically might have caused death if it were more severe.
Protocol amendment:	As defined by the International Conference on Harmonisation Tripartite Guideline for Good Clinical Practice: “A written description of a change(s) to or formal clarification of a protocol.”
Serious adverse event:	An untoward medical occurrence that at any dose (a) results in death, (b) is life-threatening, (c) requires inpatient hospitalization or prolongation of existing hospitalization, (d) results in persistent or significant disability/incapacity (e) is a congenital anomaly/birth defect (f) results in an important medical event that may jeopardize the patient and may require intervention to prevent one of the other outcomes.
Subject:	Term used throughout the protocol to denote an individual that has been contacted to participate in the clinical study, either as a recipient of the study product or as a control.
Subject Identification Number:	A unique number identifying a treatment to a subject, per the study randomization.

Suspected Unexpected Serious Adverse Reaction:	An adverse event that (a) meets the definition of a serious adverse event, (b) the nature or severity of which is not consistent with study product information in the Investigator's Brochure, and (c) there is reason to suspect that the study product caused the event.
Tolerability:	The incidence of discontinuation of study product or "drop-out" due to a treatment emergent adverse event probably or definitely related to study product.
Treatment:	Term used throughout the protocol to denote the study product or placebo intended to be administered to a subject.
Treatment-emergent adverse event:	Any event not present before the initiation of the treatments or any event already present that worsens in either intensity or frequency following exposure to the treatments.

2. INTRODUCTION

This statistical analysis plan (SAP) is being developed in conjunction with the protocol JBT101-CF-002 [Version 3.4 dated 05 NOV 2019 for all countries except France and Version 3.3 dated 05 NOV 2019 for France] sponsored by Corbus Pharmaceuticals Inc. The SAP contains detailed information to aid in the performance of the statistical analysis and reporting of the data for use in the final Clinical Study Report (CSR), including the 28-day safety follow-up period off study product.

This SAP is being written with due consideration of the recommendations outlined in the most recent International Conference on Harmonization E9 Guideline entitled Guidance for Industry: Statistical Principles for Clinical Trials and the most recent International Conference on Harmonization E3 Guideline entitled Guidance for Industry: Structure and Content of Clinical Study Reports.

This SAP describes the data that will be analyzed and the subject characteristics, efficacy, and safety assessments that will be evaluated. This SAP provides details of the specific statistical methods that will be used.

The SAP will be finalized before database lock and unblinding. If FDA requests additional analyses after the SAP is signed, those analyses will be done and added as an amendment to the SAP as additional analyses requested by the FDA. Otherwise, there will be no change to this SAP by the Sponsor after it is signed.

The statistical analysis methods presented in this document will supersede the statistical analysis methods described in the clinical protocol. If additional analyses are required to supplement the planned analyses described in this SAP, then those analyses will be completed and identified in the CSR.

3. STUDY OBJECTIVES

3.1. Primary Efficacy Objective

[figure not shown]
The primary efficacy objective is to evaluate the efficacy of lenabasum compared to placebo in the treatment of cystic fibrosis (CF) by assessing the event rate per subject per 28 weeks of new pulmonary exacerbations (PEx), using the primary definition of new PEx, comparing lenabasum 20 mg twice per day (BID) and placebo cohorts. The assessment for the primary objective occurs during the treatment period, from Day 1 to Visit 8 (Week 28).

[figure not shown]
3.2. Secondary Efficacy Objectives

The secondary efficacy objectives are assessed through or at Visit 8, as relevant. The secondary objectives will be assessed in the order below. For all analyses in the SAP, change means change from Baseline, and Visit 8 means Visit 8 or study discontinuation, unless otherwise specified.

The secondary efficacy objectives are to evaluate:

1. Event rate per subject per 28 weeks of new PEx using secondary definition of new PEx, comparing lenabasum 20 mg BID and placebo cohorts
2. Time to first new PEx using primary definition of new PEx, comparing lenabasum 20 mg BID and placebo cohorts
3. Time to first new PEx using secondary definition of new PEx, comparing lenabasum 20 mg BID and placebo cohorts
4. Event rate per subject per 28 weeks of new PEx using the primary definition of new PEx, comparing lenabasum 5 mg BID and placebo cohorts.
5. Event rate per subject per 28 weeks of new PEx using secondary definition of new PEx, comparing lenabasum 5 mg BID and placebo cohorts
6. Time to first new PEx using primary definition of new PEx, comparing lenabasum 5 mg BID and placebo cohorts
7. Time to first new PEx using secondary definition of new PEx, comparing lenabasum 5 mg BID and placebo cohorts
8. Change in Cystic Fibrosis Questionnaire – Revised (CFQ-R) respiratory symptom domain score, comparing lenabasum 20 mg BID and placebo cohorts. [REDACTED]
9. Change in forced expiratory volume in 1 second (FEV1) % predicted, comparing lenabasum 20 mg BID and placebo cohorts
10. Change in CFQ-R respiratory symptom domain score, comparing lenabasum 5 mg BID and placebo cohorts
11. Change in FEV1 % predicted, comparing lenabasum 5 mg BID and placebo cohorts

[figure not shown]

3.4. Primary Safety Objective

The primary safety objective will be assessed by treatment cohorts and by combined lenabasum cohort, for TEAEs.

1. TEAEs associated with lenabasum treatment, by treatment cohorts and combined lenabasum cohort

[figure not shown]
4. STUDY DESIGN AND PLAN AND STUDY ENDPOINTS

4.1. Study Design and Plan

This is a randomized, double-blind, placebo-controlled, multicenter, interventional, parallel-dose Phase 2b study to assess the efficacy and safety of treatment of CF subjects with lenabasum 20 mg BID and lenabasum 5 mg BID. Subjects will be randomized 2:1:2 to receive blinded study product (lenabasum 20 mg BID, lenabasum 5 mg BID, or placebo BID) for 28 weeks.

[figure not shown]
Active dosing with study product is 28 weeks. There will be 8 scheduled study visits during active dosing with study product, labeled Visits 1-8, which occur at Visit 1 and at the completion of Weeks 4, 8, 12, 16, 20, 24, and 28.

Subjects who complete Visit 8 on study product will have a Safety Follow-up Visit, labeled Visit 9, at 28 ± 7 days after Visit 8, at all study locations except for those in France.

[figure not shown]
All subjects who develop acute signs and symptoms of possible worsening respiratory disease will be asked to return to the site, as possible, for evaluation at a Possible PEx Visit.

Unscheduled Visits may be necessary to assess the subject for safety purposes unrelated to new respiratory symptoms or a PEx. If a new PEx and associated tests are recorded at an Unscheduled Visit rather than a Possible PEx Visit, that PEx information and any associated efficacy or biomarker assessments done at the Unscheduled Visit will be handled as if the Unscheduled Visit were a Possible PEx Visit.

4.1.1. Study Schematic

Figure 1: Study Schematic for JBT101-CF-002

BID = twice per day; N = number of subjects; V = visit

4.1.2. Schedule of Visits and Assessments

Schedule of clinical assessments/procedures for all subjects is presented in [Appendix 2](#). Additional assessments/procedures for France are presented in [Appendix 4](#).

The following will be assessed at all in-person visits:

- Endpoints related to PEx, CRISS, spirometry
- Concomitant medications
- Adverse events
- Study product tolerability
- Vital signs (systolic and diastolic blood pressure, pulse rate, respiratory rate, body temperature, height and weight)
- Brief Physical examination

- Contraceptive assessment and pregnancy screening for women of childbearing potential
- Complete blood count with cell differential and platelets; metabolic panel; and urine dipstick

Other assessments will be done less frequently:

- 12-lead ECGs including QT/QTc intervals (Visit 1, Visit 5, and Visit 8)
- CFQ-R questionnaire (Visit 1, Visit 5, and Visit 8)
- CRP and ESR (Visit 1, Visit 2, Visit 5, and Visit 8)
- Plasma concentrations of lenabasum and its metabolites (Visit 1, Visit 2, Visit 5, and Visit 8). Plasma concentrations and metabolites of lenabasum and ARCI-49 questionnaire will be assessed on Visit 1 before and 3.0 ± 0.5 hours after dosing.

4.1.3. Possible Pulmonary Exacerbation Visit

Subjects who experience new or worsening respiratory symptoms or who receive a prescription for a new antibiotic from a physician other than a study physician should contact the site staff and return for a Possible PEx Visit if instructed to do so. If determined that a visit is needed, a Possible PEx Visit should be scheduled as soon as possible. Though it is expected that this visit will be in person at the study sites, there may be occasions that this visit is completed over the telephone by the investigator.

If the visit is completed in person (preferred), the following assessments will be done:

- Subject-reported outcomes preferably obtained from the subject before other visit assessments.
 - CRISS questionnaire
 - CFQ-R questionnaire
- AE monitoring
- Record concomitant medications
- Vital signs and central BMI calculations
- Blood and urine tests
 - CBC with differential cell count and platelets
 - Metabolic panel
 - Urine dipstick
 - CRP, ESR and other inflammatory biomarkers
- Spirometry
- Attempt sputum collection
- Physician assessment of:
 - Brief physical examination
 - Antibiotic Use for Respiratory Signs and Symptoms Questionnaire (AUR-Q)

If the visit is completed over the telephone, the following assessments will be done:

- AE monitoring.
- Record concomitant medications.
- Physician assessment of:
 - AUR-Q

Some subjects may receive antibiotic therapy for new or worsening pulmonary symptoms or systemic symptoms from a physician other than the study investigator. In this case, site staff will ask the subject to return for a Possible PEx Visit as soon as feasible. Though it is expected that this visit will be in person at the study site, there may be occasions that this visit is completed over the telephone by the investigator. The investigator will assess the subject and complete the AUR-Q.

4.1.4. Study Population and Background Treatment for CF

The study population is males and females with CF \geq 12 years of age with FEV1 \geq 40% predicted and $<$ 100% predicted at least once within 12 months before Screening. Subjects must have 2 to 3 new PEx treated with IV antibiotic therapy within 12 months before Screening or, as an alternative, 1 new PEx treated with IV antibiotics and at least 1 PEx treated with oral antibiotics within 12 months before Screening.

Subjects should be considered stable and on stable medication for treatment of CF prior to Visit 1. For example, subjects are allowed use of prophylactic antibiotics and CFTR-modulating medications if they are on stable doses within 28 days of Visit 1. A subject with an increase in dose or initiation of any new chronic therapy for CF within 28 days of Visit 1 is not eligible for enrollment. Changes in treatment of CF after study start are allowed when those changes are in the subject's best medical interest, as assessed by the treating physician. Sensitivity analyses will be performed to assess potential impact of treatment at Baseline with drugs that might reduce rate of PEx, including concomitant CFTR-targeting medications, azithromycin, prophylactic antibiotics, and dornase alfa on the primary and first secondary efficacy outcome.

4.1.5. Target Enrollment

Target enrollment is 415 eligible subjects. Assuming a screen failure rate of \sim 15%, \sim 490 subjects will be screened to identify a target of 415 eligible subjects who will be enrolled at up to \sim 100 multi-national sites. Assuming a \sim 15% drop-out rate, \sim 352 subjects will complete the study.

4.1.6. Screening

Screening can occur up to 28 days before Visit 1. A subject that has screen failed may re-screen later at the discretion of the site investigator. A new subject code will be allocated at re-screening.

4.1.7. Duration of Study

The intended duration of active dosing is 28 weeks (through Visit 8).

4.1.8. Masking, Blinding, and Unblinding

Dosing will be done in a double-blinded, randomized, placebo-controlled manner.

Lenabasum and placebo capsules have identical physical appearance and will be packaged, labeled, and handled so that subjects and study staff are not able to distinguish between them. Identical assessments and procedures will be followed during the study for subjects assigned to lenabasum and placebo cohorts.

All study subjects and the site study staff, including the investigators who will do safety and clinical assessments, qualified designees, study nurses, and study coordinators at the sites, will remain blinded to treatment assignment during the entire study, until after the database is locked. If the treatment allocation for a subject otherwise becomes known to the investigator or other study staff at the site prior to database lock, the investigator or designee must notify Corbus immediately.

In an identical manner, all Corbus medical and clinical operations staff associated with the conduct of this study will remain blinded to treatment assignment during the entire study, until after the database is locked.

Corbus clinical supplies personnel will be unmasked to the study product randomization. They are required not to reveal randomization information to others, unless a formal unmasking of information for a given subject is undertaken for safety reasons.

A limited number of contract laboratory personnel who perform and interpret assays of lenabasum concentrations and metabolites, as well as an independent statistician assigned to the Data Monitoring Committee (DMC), will be unmasked. These unmasked external personnel will not be associated with the clinical conduct of the study and will not reveal to any clinical personnel involved in the study the treatment to which a subject is assigned.

In the event of a safety concern that requires unblinding of treatment assignment for an individual subject, the investigators will have 24-hour access to an Interactive Web Response System (IWRS) through which the code can be broken for that subject. Systematic procedures for unblinding through the IWRS will be described in a manual supplied to the site. In all circumstances other than a medical emergency, unblinding will be done only by the Medical Monitor, and only after discussion with the requesting investigator. In an emergency, investigator will be able to unblind the subject, but should discuss with the medical monitor as soon as feasible.

4.1.9. Randomization, Stratification Factors, Treatment Cohorts, and Dosing

Before dosing on Visit 1 (Day 1), eligible subjects will be randomly assigned using an Interactive Web-based Response Technology system to one of three treatment cohorts, based on a randomization schedule prepared by an independent biostatistician who was not involved in the day-to-day conduct of the study. The randomization will be stratified by number of previous new PEx requiring IV antibiotics in the previous year (“1 vs 2 or 3”; however, this changed approximately midway of study to “1 or 2 vs 3”, See [Section 13](#)), FEV1 % predicted at baseline (< 70; ≥ 70) and location of site (United States; Non-United States).

Subjects will be randomized in a 2:1:2 ratio to 1 of 3 treatment cohorts:

- Cohort 1: Lenabasum 20 mg BID, n = 166

- Cohort 2: Lenabasum 5 mg BID, n = 83
- Cohort 3: Placebo BID, n = 166

Twice per day dosing consists two doses each day with at least 8 hours between doses. Subjects will self-administer study product, which will be taken by the oral route and with no requirement as to fed or fasting state. Phase 1 data showed little impact of the fed-state on exposure to lenabasum, and subjects in all Phase 2 studies to date have taken lenabasum without regard to fed state.

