6.3. Sample Size and Power Considerations

The study is expected to enroll approximately 415 subjects, with ~166 subjects each in the lenabasum 20 mg BID and placebo BID cohorts and ~83 subjects in the lenabasum 5 mg BID cohort (accounting for an approximate 15% dropout rate). The study provides 80% power to detect a significant difference between the lenabasum 20 mg BID dose and placebo in the primary endpoint (PEx event rate) at a two-sided alpha of 0.05. This is based on an event rate ratio of 0.65 (a 35% event rate reduction in the lenabasum group), when the event rate in the control group is 0.80.

This also provides 90% power to detect a significant difference between lenabasum 20 mg BID and placebo BID in the secondary endpoint of time to first PEx. This is based on an estimate of the probability of an event (PEx) in the placebo group of 0.60, an estimated hazard ratio of 0.60 (risk reduction 0.40), and the probability of an event in the lenabasum group of 0.36.

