9.4. Primary Efficacy Analysis

9.4.1. Event Rate of New Pulmonary Exacerbations per Subject per 28 Weeks by Primary Definition

The primary efficacy endpoint is the event rate of new PEx per subject per 28 weeks using the primary definition (Sections [4.2.1](#) and [5.1](#)), for the comparison of lenabasum 20 mg BID cohort to the placebo cohort, in the mITT population, through Visit 8 (Week 28) which is the treatment period.

The event rate per subject per 28 weeks of new PEx will be compared between the lenabasum and placebo cohorts using a Poisson regression model with effects of treatment and log (subject treatment exposure duration), adjusting for baseline subject characteristics of site location (United States; other countries), number of new PEx requiring IV antibiotics in the previous year (1; 2; 3); FEV1 % predicted (< 70; \geq 70); and baseline CFTR-targeting medications use (Yes; No – taken concomitantly on Day 1, baseline), and based on the mITT population.

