9.5.4. Continuous Variable Secondary Endpoints

Continuous variable secondary efficacy endpoints other than PEx event rate per subject per 28 week endpoints, (change from baseline in CFQ-R respiratory symptom domain score for adolescents and adults, and change in FEV1 % predicted, change in CRISS score) will be analyzed using a parametric mixed model repeated measures (MMRM). The MMRM model will include treatment, site location (United States; other countries), number of new PEx requiring IV antibiotics in the previous year (1; 2; 3); FEV1 % predicted (< 70; \geq 70); Baseline CFTR-targeting medications use (Yes; No), visit, and treatment-by-visit interaction as fixed effects, and baseline of response variable as a covariate. The parametric MMRM will use unstructured covariance matrix. Least squares means, least squares mean differences and associated 95% CI, and 2-sided p-values will be provided.

If the data are not normally distributed, then nonparametric MMRM analyses will be performed using a ranking strategy that relaxes the assumption of normality. The ranks will be assigned by a visit such that the same rank will be assigned across all treatment cohorts and placebo for a dependent variable measurement. The rank transformed nonparametric model will be analyzed including the fixed and random effects similar to the parametric MMRM model. The nonparametric MMRM model will use unstructured covariance matrix. Least squares means, least squares mean differences and associated 95% CI, and 2-sided p-values will be provided.

Two-sample t-test will be used to compare means for change from Baseline within the same group. Wilcoxon rank sum test analyses will be used to compare medians for change from baseline within the same group, in case of shift from the central tendency. Two-sided p-values will be provided.

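### The PEx rate and Cox models use baseline FEV1 % predicted only as <70/≥70 and adjust for one of four named drug classes, leaving a small, nearly free gain in precision unused

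*SAP*

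**What the plan says.** - **Models.** SAP 9.4.1 adjusts the primary Poisson regression for site location, prior PEx requiring IV antibiotics, "FEV1 % predicted (< 70; \geq 70); and baseline CFTR-targeting medications use". Section 9.4.2 repeats this list for the sensitivity models, 9.5.1 applies the primary method to the other PEx rate endpoints, and 9.5.3 uses the same covariates in the Cox model. No continuous FEV1 term appears in any of them.
- **Strata.** The cut at 70 comes from randomisation (4.1.9), which is stratified on prior PEx, "FEV1 % predicted at baseline (< 70; ≥ 70) and location of site".
- **Range and availability.** Eligibility (4.1.4) requires a value from 40 to under 100% predicted at least once in the 12 months before Screening. FEV1 % predicted is a baseline variable in 7.1.
- **Drugs.** Section 4.1.4 promises sensitivity analyses, on the primary and first secondary outcomes, of Baseline treatment with "drugs that might reduce rate of PEx, including concomitant CFTR-targeting medications, azithromycin, prophylactic antibiotics, and dornase alfa". Section 13 records that CFTR-targeting use was added to the models. The other three classes are neither strata nor covariates.
- **Sensitivity list.** The visible 9.4.2 contains per-protocol and negative binomial analyses only, and 9.5.2 refers back to it.
- **Continuous endpoints.** The MMRM in 9.5.4 keeps the two-level FEV1 term and adds "baseline of response variable as a covariate".

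**The concern.** A two-level FEV1 term treats subjects at 40 and 69% predicted as alike and separates 69 from 70. If PEx risk changes steadily with FEV1, the risk differences within each stratum go unmodelled. The same holds for three therapies that the SAP itself regards as possibly lowering the PEx rate.

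Two consequences follow. The estimate is noisier than it needs to be, because within-stratum and drug-use imbalances between arms feed into the rate ratio. And the primary test uses a plain Poisson standard error, which takes variance equal to the mean; unmodelled risk differences make that standard error too small. The primary result gates the eleven ordered secondary tests (9.3, 4.2.2), so its calibration matters.

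**Working it through.** **Inputs from SAP 6.3.** Test level: "in the primary endpoint (PEx event rate) at a two-sided alpha of 0.05". Power: "The study provides 80% power to detect a significant difference between the lenabasum 20 mg BID dose and placebo". Effect: "event rate ratio of 0.65 (a 35% event rate reduction in the lenabasum group), when the event rate in the control group is 0.80", so 0.80 × 0.65 = 0.52 on lenabasum. Size: "166 subjects each in the lenabasum 20 mg BID and placebo BID cohorts", with 15% dropout, so 0.85 × 166 ≈ 141 completers per arm.

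**Step 1: the plan's own figure.** For a Wald test of the log rate ratio, n per arm = (1.960 + 0.842)² × (1/0.80 + 1/0.52) / (ln 0.65)² = 7.849 × 3.173 / 0.1856 = 134.2, or 158 after dividing by 0.85. With 141 per arm the standard error is √(3.173/141) = 0.150, and power = Φ(0.4308/0.150 − 1.960) = 81.9%. The stated 80% reproduces. With 166 per arm the variance is 3.173/166 = 0.0191 (standard error 0.138). Expected events: 166 × 0.80 + 166 × 0.52 = 219.

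**Step 2: what the cut keeps.** The FEV1 distribution is not given. Assuming a normal (mean 65, SD 16) truncated to 40–100, the SD is 13.5, the cut explains 67% of the variance, and the pooled within-stratum SD is 13.5 × √(1 − 0.67) ≈ 7.7. For a uniform distribution on 40–100 the cut explains 75%. So 25–33% of the FEV1 variance is lost.

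**Step 3: chance imbalance left on the log rate ratio, 166 per arm.** For FEV1, SD = (ln R / 10) × 7.73 × √(2/166), where R is the rate ratio per 10 points lower. For each drug at 50% use, SD = |ln R_d| × √(0.25 × 2/166), where R_d is the drug's rate ratio. Combined SD = √(FEV1 SD² + 3 × drug SD²), taking the drugs as independent. Shares are squared SDs over 0.0191.

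| Assumption (R; R_d) | FEV1 SD | SD per drug | Combined SD | Share, FEV1 alone | Share, all four | 95% shift factor |
|---|---|---|---|---|---|---|
| Weak (1.1; 0.9) | 0.0081 | 0.0058 | 0.013 | 0.3% | 0.9% | 1.03 |
| Moderate (1.2; 0.8) | 0.0155 | 0.0122 | 0.026 | 1.3% | 3.6% | 1.05 |
| Strong (1.3; 0.7) | 0.0223 | 0.0196 | 0.041 | 2.6% | 8.6% | 1.08 |

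**Step 4: simulation with 141 per arm.** 2000 trials per scenario, stratified on the FEV1 cut, same assumptions. Each cell gives the model with dichotomised FEV1, then the model with continuous FEV1 and three drug terms.

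| Assumption | Type I error | Power | SD at ratio 1 | SD at ratio 0.65 |
|---|---|---|---|---|
| Weak | 5.7 / 5.2% | 84.2 / 84.4% | 0.1356 / 0.1362 | 0.1470 / 0.1472 |
| Moderate | 5.0 / 4.8% | 83.6 / 83.3% | 0.1356 / 0.1326 | 0.1494 / 0.1475 |
| Strong | 6.5 / 4.8% | 80.2 / 81.0% | 0.1368 / 0.1312 | 0.1616 / 0.1532 |

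Monte Carlo error on type I error is about √(0.05 × 0.95/2000) = 0.5 points. The mean estimated ratio was 0.647 to 0.652 under both models (truth 0.65). The variance reduction, 1 − (SD ratio)², is nil in the weak case, 2–4% in the moderate case and 8–10% in the strong case. If none of the added terms is prognostic, power goes from 83.3% to 82.6%, which is the price of adding them.

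**Step 5: a second simulation with 166 per arm.** 3000 trials, FEV1 mean 70, SD 16, clipped to 40–100, 20% rate change per 10 points, drug rate ratio 1.5 each at 50% use. SDs for the dichotomised model, plus continuous FEV1, plus drugs: 0.147 / 0.146 / 0.142 at ratio 0.65 and 0.132 / 0.131 / 0.124 at ratio 1. Continuous FEV1 alone therefore saves 1–2% of variance. With the drugs the saving is about 7% and 12%, and rounding of the SDs allows up to 13%. Type I error was 6.5 / 6.4 / 5.3%. With weak effects (10% per 10 points, drug rate ratio 1.2) the gain was under 1%.

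**Step 6: why type I error moves.** In the strong case of Step 4 the mean Poisson standard error under the null was 0.1310 against a true SD of 0.1368. The effective critical value is 1.96 × 0.1310/0.1368 = 1.877, a two-sided level of about 6.1%. With the extra terms it is 1.96 × 0.1320/0.1312 = 1.972, about 4.9%.

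**Limits.** Neither simulation included prior PEx, site location or CFTR use, which may absorb part of the same risk. Drug use was independent of FEV1, no further overdispersion was added, and the Cox model was not simulated.

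**The case against.** The strongest reply is that this is a preference about covariates. Stratifying on a two-level cut and carrying the stratum into the model is standard practice. It also balances FEV1 across 70, so only within-stratum imbalance remains. That stands: 4.1.9 is not in error, and the point concerns the models in 9.4.1 and 9.5.3.

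A reader might infer that the primary rate ratio is biased. The documents do not support that. Randomisation makes the estimate right on average, the log rate ratio does not change meaning when covariates are added to a Poisson model, and the simulated means confirm it. What remains is variance and calibration of the standard error.

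A reader might also infer that the SAP ignores the three other drug classes. It does not: 4.1.4 promises sensitivity analyses for them. The visible 9.4.2 and 9.5.2 do not carry that out, but some sections are not in the text at hand (11.4 cites a 9.6.3 that is not shown), so absence from the whole plan cannot be claimed.

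Further, the drug gain rests on assumed strength, prevalence and independence. Azithromycin is itself an antibiotic and may overlap with prophylactic antibiotics, and 4.1.4 says only that these drugs might reduce PEx. That stands too, and it makes the drug terms the secondary part of the fix. A linear FEV1 term assumes log-linearity, which the documents do not establish; keeping the stratum term softens this. The MMRM in 9.5.4 shows the same structure already in use, but baseline of the response is the usual covariate there and proves nothing about a count model.

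Finally, the negative binomial sensitivity models address extra variation generally. They do, but they are not the primary test.

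**Conclusion.** The point holds as a modest improvement to the covariate set. The PEx rate and Cox models discard part of a baseline measurement already in hand, and treat one of four named drug classes differently from the other three without a reason in the visible text.

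The size depends on prognostic strengths that the SAP does not give. With weak effects the gain is under 1% of variance. Continuous FEV1 alone brings 1–2% if the rate changes 20% per 10 points (2.6% at 30% per 10 points, by Step 3). The roughly 7–13% with the drug terms requires each to be strongly prognostic, used by about half the subjects and independent of the others. Power changes by about 1 point or less throughout. An effect on type I error is visible only under the strong assumptions (6.5% to about 5%); elsewhere it lies within simulation error. A claim that the primary test is materially miscalibrated would go beyond this evidence.

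**What to change.** **Main change.** In 9.4.1, 9.4.2, 9.5.1 and 9.5.3, keep the <70/≥70 term and add baseline FEV1 % predicted as a continuous covariate.

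**Secondary change.** Define Day 1 use (Yes/No) of azithromycin, prophylactic antibiotics and dornase alfa in the way CFTR-targeting use is defined, and state how azithromycin taken as prophylaxis is counted. Enter the three indicators in the main models or, at minimum, write them into 9.4.2 and 9.5.2 as the sensitivity analysis promised in 4.1.4. Either change can be made without the other.

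**Cost.** SAP wording, one degree of freedom for FEV1 and three for the drugs, against about 219 expected events. FEV1, prophylactic antibiotics and concomitant medications are already recorded (7.1, 7.3, 8.1). In the Cox model, added covariates can shift the hazard ratio being estimated, so the set must be fixed in advance. Section 2 allows no sponsor changes after signature, so the text must change before the SAP is signed, and in any case before unblinding.
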